1.3 Predictive neural and behavioral biomarkers for clinical placebo

Summary of main findings from Phase 1 Report:

1. Using the smart phone pain ratings and within subject permutation method provides a robust method for classifying placebo responders and non-responders.
2. Three emotion-related personality outcome measures (MAIA-not worry, MAIA-emotion, ERQ-suppress) together predict future placebo response at 94% accuracy. These measures are also correlated to questionnaires regarding alternative and complementary medicine including MISS (suggestibility), HCAMQ (holistic subscale), and MLHC (health locus of control).
3. Resting state fMRI brain network information sharing between the frontal cortex and somatosensory cortex predicts placebo response at a very high accuracy.
4. Somatosensory cortex grey matter density predicts placebo response.

5. Brain white matter myelination properties do not predict placebo response.
6. Brain grey matter neurite orientation properties do not predict placebo response.
7. Limbic brain right to left asymmetry predicts placebo response.
8. The combined brain and personality final model predicts placebo response at 94% accuracy.

Conclusions from Phase 1 report:

1. The primary conclusion of these results is our ability to demonstrate that clinical placebo response is predictable from personality and from brain properties.
2. Identified personality parameters are distinct from those hypothesized in healthy subjects for experimental manipulations, and are consistent with CBP involving emotional circuitry. The relationship between these and attitudes to alternative medicine suggest common underlying mechanisms.
3. Functional information sharing results are based on a specific hypothesis we derive from our earlier similar study conducted in osteoarthritis patients, suggesting shared mechanisms of clinical placebo response predictive circuits.
4. The cortical gray matter prediction of placebo seems linked to the functional information sharing circuit and probably reflects inter-related measures.
5. The fact that we did not find a whole-brain contrast in white matter myelination properties to predict placebo response was expected and not surprising. It is possible that the white matter connectivity between the functional networks may still be distinct (remains to be tested).

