2.0 STUDY OBJECTIVES

2.1 Primary and Secondary Objectives

- 2.1.1 To evaluate the interaction between placebo response and active treatment in individuals classified as placebo responders vs non-responders. Individuals in the No Treatment group will be used as a negative control to control for regression to the mean, duration of pain, and other potential confounds.

Hypothesis: Brain functional and anatomical properties between groups after 6 weeks of treatment will identify separate circuitry for placebo analgesia and active treatment analgesia; and these groups will show distinct time courses and magnitudes of analgesia.

- 2.1.2 To test and validate brain imaging and personality parameters identified in Phase 1 that predict the propensity for placebo response and use the results to classify participants into responders vs non-responders before study intervention.

Hypothesis: Brain- and behavioral- based parameters identified as markers of placebo response in the first phase of the study will accurately predict potential responders from non-responders at first scan. The classification before study intervention will closely correspond to the responses observed at the end of treatment period.

- 2.1.3 To identify gender dependence of placebo analgesia propensity and examine brain and personality gender differences that underlie the seeming higher propensity of females for placebo response.

Hypothesis: Sexual dimorphism of the human brain and behavioral/personality differences may have a potential interaction effect and predisposition on placebo propensity. We expect to identify gender-specific biomarkers that are sexually dimorphic with regard to placebo response.

- 2.1.4 Classification of placebo responders versus non-responders for 2.1.2 will be based on Equation 1 below:

$$p = (e^{f(x)}) / (e^{f(x)} + 1)$$

$$f(x) = -3.3586 + 1.6676 * \text{Maia_Emotion} - 0.2127 * \text{Erq_Suppress} + 34.8608 * \text{sign_permutation}$$

where a probability (p) <0.5 = predicts non-responder and a probability (p) ≥0.50 predicts responder.

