2.3 Endpoints

- 2.3.1 Endpoint for primary objective: (1) Placebo response (defined as > 20% reduction in pain intensity following placebo treatment, or defined from pain app ratings using permutation with 0.05 p-value cut-off) versus active treatment response (reduction in pain intensity following naproxen/omeprazole treatment)
- 2.3.2 Endpoints for secondary objective: (1) Testing the specificity and sensitivity of the brain and behavioral parameters from Phase 1, in combination with the TOPPP developed from the study interviews, as predictive markers for response in Phase 2. These parameters will be considered validated if together are at least 80% accurate in stratifying responders from non-responders.
- 2.3.3 Endpoint for gender objective: (1) Testing for females showing higher incidence of placebo response using combined outcomes from phase 1 and phase 2 data.

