- Visit 2 (week -1): Baseline Scan (90 min). Approximately 14 days after visit 1, participants will return for their second visit. If a VAS score of > 5 mm on average over the course of the visit 1-visit 2 rating period is calculated and no changes in clinical status are reported or found, they complete a battery of questionnaires and undergo MRI procedures (anatomical and functional scans). Subjects will be queried about changes to health experienced since the last visit and asked if they exceeded 4 acetaminophen per day. In addition one of the pictures for visit 2, 4, and 5 will be conducted (see section 13.III). They will be asked to continue their phone/computer app ratings and return in approximately one week for visit 3. Participants will receive only rescue medication in sufficient quantities until the next visit. Additionally, participants will be randomized into a treatment versus no-treatment group at this time (information that the pharmacy will produce and keep).
- Interim between Visit 2 and Visit 3: Group classification Based on Predicted Response

In between visits 2 and 3, participant's scans will be analyzed by extracting the functional connectivity between frontal and sensorimotor networks (called "sign permutation" in Equation 1) and 2 questionnaire subscores will be calculated (MAIA emotion and ERQ suppression in Equation 1); all 3 parameters will then be entered into Equation 1. Based on the results of the model specified on page 10, participants will be classified as either placebo non-responders (probability < 0.5) or placebo responders (probability \geq 0.5).

After baseline scan, the subjects' MR images and data will be collected by research personnel and then will be given to a single member, the blinded assessor ([name]) who will have no interaction with the participants, therefore will remain blinded. The research personnel responsible for conducting the visit will download the MAIA and ERQ questionnaires from the REDCap database and calculate the scores for MAIA-Emotion and ERQ-suppression subscales to be used in the model.

(1) All MR images collected at the baseline scan will be uploaded to the server and pre-processed within 24 hours of the visit using our in-house pipeline.

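### The 80% validation rule judges brain and questionnaire markers only jointly, so a scan value redundant with the questionnaires could be declared a validated brain marker

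*Combined protocol and SAP*

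**What the plan says.** Objective 2.1.2 is "To test and validate brain imaging and personality parameters identified in Phase 1". The matching endpoint in 2.3.2 is "Testing the specificity and sensitivity of the brain and behavioral parameters from Phase 1, in combination with the TOPPP developed from the study interviews", and its only pass criterion is "These parameters will be considered validated if together are at least 80% accurate in stratifying responders from non-responders". Section 2.2 validates the biomarkers through the same stratification before treatment. Section 8.2.7 applies only the final Phase 1 model, which is Equation 1 in section 2.1.4. Section 5.2.1 gives its content, with the connectivity value as the third input: "2 questionnaire subscores will be calculated (MAIA emotion and ERQ suppression in Equation 1); all 3 parameters will then be entered into Equation 1".

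Section 1.3 reports three Phase 1 results that bear on this:

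- Questionnaires alone: "Three emotion-related personality outcome measures (MAIA-not worry, MAIA-emotion, ERQ-suppress) together predict future placebo response at 94% accuracy".
- Frontal–somatosensory connectivity: it "predicts placebo response at a very high accuracy", with no figure.
- Both combined: "The combined brain and personality final model predicts placebo response at 94% accuracy".

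Other sections look at the parts separately:

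- Section 8.2.6 intends to validate a personality model in Phase 2, either the Phase 1 model or a close variant. It sets no pass mark and no comparison with Equation 1.
- Section 8.2.5 intends to re-test limbic asymmetry, which is not in Equation 1.
- Section 4.4 prints a mixed model for daily pain that carries SIGN_PER, and SIGN_PER by day, beside both questionnaire scores and their day terms.

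**The concern.** The objective names two kinds of marker, but the decision rule returns one verdict for both. If the questionnaires carry the prediction and the connectivity value only repeats their information, Equation 1 can clear 80% and the brain parameter is declared validated with it.

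Phase 1 gives reason to take this seriously, because the combined model is reported at the same accuracy as a questionnaire set with no scan in it. The study title and the Phase 1 conclusions put brain properties forward as predictors. Section 1.4 regards imaging as impractical for clinical decisions. A reader of the results will therefore want to know whether the scan tells more than the questionnaires do, and the rule cannot answer that.

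**Working it through.** **Inputs**

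- Pass mark: accuracy of at least 80% (2.3.2).
- Randomized: 210 at 3:3:1, with attrition of about 33% and a final N of 140 (5.3).
- Alternative placebo arm sizes: 40, or 60 with the gender supplement (8.1.1).
- Phase 1 accuracy: 94% for three subscales and 94% combined (1.3).

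**1. The plan's own figures.** The sample size reproduces: 210 × (1 − 0.33) = 140.7, against the stated 140. Placebo completers are then 140 × 3/7 = 60. The two 94% figures cannot be reproduced, because the documents give no counts, confusion table or cross-validation detail. Section 2.3.2 does not say in whom the 80% is judged. I assume placebo completers, since placebo response is observed there.

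**2. Are the two 94% models comparable?** The questionnaire model uses MAIA-not worry, MAIA-emotion and ERQ-suppress. Equation 1 uses MAIA-emotion, ERQ-suppress and connectivity. One subscale was exchanged for the scan value, so neither model contains the other. The accuracy of the two retained subscales alone is not given.

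**3. Pass probability if the combined model is only as accurate as the questionnaires.** For accuracy a and n participants, P(pass) = P(X ≥ 0.8n), with X binomial(n, a).

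| n (bar) | a = 85% | a = 90% | a = 94% |
|---|---|---|---|
| 40 (32) | 0.865 | 0.985 | 0.9995 |
| 60 (48) | 0.894 | 0.994 | >0.9999 |
| 90 (72) | 0.926 | 0.999 | about 1.00 |

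This is the case of a scan value that neither helps nor harms. The conclusion does not depend on which arm size applies.

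**4. Pass probability if the scan value is pure noise.** Equation 1 gives sign_permutation a fixed weight of 34.8608, so an uninformative value adds noise to the score. Under a binormal model, combined accuracy = Φ(z(q)/√(1 + k²)). Here q is the accuracy of the questionnaire part and k is the SD of the noise term divided by the within-class SD of the questionnaire score. The value of k is an assumption, because the SD of the connectivity value is not given. For example, with q = 94% and k = 1: Φ(1.555/1.414) = 86.4%. Pass probabilities at n = 60:

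| q | k = 0.5 | k = 1.0 | k = 1.5 | k at which expected accuracy reaches 80% |
|---|---|---|---|---|
| 94% | 0.999 | 0.94 | 0.62 | 1.55 |
| 90% | 0.97 | 0.71 | 0.30 | 1.15 |
| 85% | 0.75 | 0.34 | 0.10 | 0.72 |

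**5. Can a paired accuracy comparison settle it?** A two-sided exact McNemar test with all discordant pairs in one direction has p = 2 × 0.5^d: 0.0625 for d = 5 and 0.031 for d = 6. At least 6 questionnaire errors, all corrected, are therefore needed. At 94% and n = 60, 60 × 0.06 = 3.6 errors are expected, and P(6 or more) = 0.15. That is the upper bound on power even if the combined model is perfect (0.03 at n = 40). At questionnaire accuracy of 90%, 85% and 80% with n = 60, the bound is 0.56, 0.90 and 0.99.

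**The case against.** The strongest reply has four parts.

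- **A conditional look is already planned.** A reader might infer that no analysis ever examines connectivity given the questionnaires. Section 4.4 contradicts that: the SIGN_PER terms are estimated beside both questionnaire scores. This stands. However, that model concerns daily pain rather than responder status, has no treatment term as printed, leaves room for alternative models, has no pass criterion, and is not tied to 2.3.2.
- **The rule does not pass whatever the scan contributes.** A reader might infer that it does, provided the questionnaires hold up. The fixed weight in Equation 1 means that a noise value costs accuracy, and step 4 shows that it can fail. This stands. The exposure that remains certain is to a redundant value.
- **Equal 94% figures do not prove a useless scan.** A reader might infer that they do. Since the models are not nested, the scan may be replacing what MAIA-not worry supplied. This stands. What remains is that no gain over the three-subscale set is documented.
- **Predictive validity is not incremental value.** Section 2.2 expects the brain circuits to be reflected in personality and expectation measures, so a truly predictive marker may add little to them. Section 1.4 uses the impracticality of imaging to argue for a self-report tool, not for adding a scan. This stands against any rule that the marker must add to the questionnaires to count as validated at all. It does not defend a single joint verdict for two kinds of marker.

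This is also a secondary endpoint, which limits the weight of the point.

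**Conclusion.** The point holds in a limited form and should be addressed. The joint criterion can validate Equation 1 as a classifier, but it cannot support a separate statement about the brain parameter. If the scan value is redundant, so that combined accuracy equals the questionnaires' accuracy, the rule still declares both validated with probability 0.89, 0.99 and about 1.00 at 85%, 90% and 94%. This rests on about 60 placebo completers and a bar of 48. If the value is pure noise, the outcome depends on k and may be failure.

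The documents support neither the claim that the scan adds nothing nor the claim that it adds something. The plan has no step, tied to the validation decision, that would tell the two apart.

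**What to change.** Amend 2.3.2 and 8.2.7 before unblinding:

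1. State that the 80% rule validates the combined classifier, Equation 1, and nothing narrower.
2. In the placebo arm, pre-specify a likelihood-ratio test comparing logistic models for observed responder status with and without sign_permutation, both containing MAIA_Emotion and ERQ_Suppress.
3. In the same participants, report accuracy and AUC with 95% CIs for the questionnaire-only model, the brain-only marker and Equation 1. Give the paired differences as supportive only. Lock the questionnaire-only coefficients from Phase 1, and a cut-off for the brain-only marker, before unblinding; the documents print neither.
4. Claim that the scan adds to the questionnaires only if the likelihood-ratio test supports it, and name the two subscales it was conditioned on. Do not require incremental value before calling the marker predictive on its own.
5. Say how the SIGN_PER terms in section 4.4 bear on validation, if at all.

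No new data are needed: MAIA and ERQ are scheduled for everyone at visit 1 and the scan at visit 2. The costs are that the brain claim may weaken and that power for an accuracy gain is low near the ceiling (step 5), which is why the likelihood-ratio test should carry the inference. Its own power cannot be computed, because the documents give no effect size for sign_permutation given the questionnaires.

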The proposed study of placebo analgesia in CBP is justified because there is currently no single empirically supported treatment for CBP pain. Given our ignorance of basic properties of placebo analgesia, such as reproducibility within individuals, duration of the response, and interactions with active medications, short-term studies are appropriate to address these issues. Furthermore, the active medication control group taking naproxen will receive a standard-of-care treatment, and all participants will be allowed to take acetaminophen (rescue medication) as needed. Although placebo is associated with side effects, there is evidence that symptom base rates associated with placebo are lower than those observed in the general population (Barsky et al., 2002). For these reasons, the scientific benefits outweigh potential risks that are attributable to placebo use.

In phase 1 of this grant, we expect to confirm our hypothesis that about 50% of CBP patients respond to a 2 weeks placebo treatment using smartphone to collect daily measurements of chronic pain intensity. On average and so far, participants showed very good compliance rate on the use of smartphone, reaching on average of 75%. Using these continuous measurements of chronic pain intensity, we expect to demonstrate that patients responding to a placebo treatment will show a robust reduction of about 25% of their pain intensity compared to their visit 1 to visit 2 ratings. This would confirm our preliminary observations that about half of enrolled CBP will respond to placebo treatment and that expected pain analgesia will be clinically meaningful.

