4.2 Duration of Therapy

Treatment may continue for **6 weeks** or until:

- Inter-current illness prevents further administration of treatment;
- Unacceptable adverse event(s);
- Patient decides to withdraw from the study; **OR**
- General or specific changes in the patient's condition render the patient unacceptable for further treatment in the judgment of the investigator.

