8.1.2 Sample Size and Accrual

Statistical power can be estimated based on the Cohen's d effect sizes for differences in pain with 6 weeks of treatment. For responders, based on our preliminary results, we anticipate a mean decrease of 2.5 units on a 0-10 scales with an estimated SD of 3, which results in an effect size estimate of 0.83. In non-responders, the mean decrease in pain is negligible and we do not expect to have enough power to detect this.

Power analyses in G*Power 3.1.3 indicated that we will have ample power to detect pre-to-post changes within a group; with an estimated effect size of $d = 0.8$, power would exceed 95% with a sample of 23 participants. In terms of a between-group comparison, assuming an effect size estimate of $d = 0.8$ across groups, power would exceed 95% for a sample size of $n = 42$ per group. Thus, the total sample size of 210 would provide for adequate power, even accounting for

potential dropout and/or lower-than-expected effect sizes. Assuming that we recruited 70 participants per group, for example, would mean that we could detect between-group effects as small as $d = 0.5$ with power exceeding 80%.

Power analysis for gender: The preliminary gender analyses from phase 1 subjects provide the means to calculate the power necessary for detecting gender effects in placebo propensity. The original sample sizes from phase 1 were based on treating gender and age as covariates of no interest. Based on an anticipated medium-sized effect using Cohen's conventions (Cohen, 1992), calculations in `chi2power` in Stata indicated that for $n=82$ and for $\alpha = 0.05$ we obtain power = 0.31. Instead if we double the number of subjects then we reach adequate detection power: assuming that males have 30% while females 50% placebo incidence rate, for $\alpha = 0.05$ and $n=160$ we obtain just adequate power = 0.74. Therefore all data from phase 1 and 2 will be combined to assess effect of gender on placebo response.

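### The gender test pools Phase 2 with Phase 1 subjects already analysed by gender, without a phase stratum, so it cannot serve as an independent confirmation of a female-higher hypothesis

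*Combined protocol and SAP*

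**What the plan says.** Objective 2.1.3, listed among the primary and secondary objectives, refers to "the seeming higher propensity of females for placebo response". Its endpoint in 2.3.3 is "Testing for females showing higher incidence of placebo response using combined outcomes from phase 1 and phase 2 data".

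Section 8.1.2 gives the history. On the Phase 1 design it says: "The original sample sizes from phase 1 were based on treating gender and age as covariates of no interest". It then says: "The preliminary gender analyses from phase 1 subjects provide the means to calculate the power necessary for detecting gender effects in placebo propensity". It reports power of 0.74 for n = 160 at alpha 0.05, "assuming that males have 30% while females 50% placebo incidence rate", and concludes: "Therefore all data from phase 1 and 2 will be combined to assess effect of gender on placebo response". Power is the only reason given for pooling.

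Section 8.2 repeats the pooling. It makes the exploratory brain and personality analyses by gender conditional on the hypothesis being validated. It names no phase term, no phase-by-gender check and no analysis of gender in Phase 2 alone.

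On exposure, Section 1.2 expects for Phase 1 that "about 50% of CBP patients respond to a 2 weeks placebo treatment". For Phase 2, Section 4.2 says "Treatment may continue for 6 weeks or until" one of the listed events occurs. The responder rule in 2.3.1 and 6.0 sets no common assessment window for the two phases.

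**The concern.** Data that have already been examined by gender are counted again in the test of the gender hypothesis. If Phase 1 leaned towards females, the pooled test starts part of the way to significance, and Phase 2 needs to add less than a fresh test would require. A positive result would then be reported as validation and would open the downstream gender analyses.

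The plan is stricter with its other Phase 1 findings. The brain and personality markers are to be checked in a separate cohort of new patients (Study Summary, Section 2.2). Gender gets no such check.

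A second, smaller issue is that pooling without a phase stratum lets a between-phase difference enter the gender contrast. This happens if response rate and sex mix both differ between phases.

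**Working it through.** **1. The plan's power figure.** Inputs from 8.1.2: 30% versus 50%, n = 160, alpha 0.05. Assumed: two-sided test, 80 per sex (sidedness and sex split are not stated).

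- SE under the null = sqrt(0.40 × 0.60 × 2/80) = 0.0775
- SE under the alternative = sqrt((0.30 × 0.70 + 0.50 × 0.50)/80) = 0.0758
- Power = Φ((0.20 − 1.96 × 0.0775)/0.0758) = Φ(0.635) = 0.737

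This reproduces the stated 0.74.

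**2. What re-using Phase 1 does.** With two phases of about equal size, pooled z ≈ (z1 + z2)/√2. A significant female-higher result needs z2 > 1.96 × √2 − z1 = 2.77 − z1. With no gender effect in Phase 2, z2 is standard normal.

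The documents do not give z1, so it is varied. The largest value supposes that Phase 1 showed exactly the planning rates with 41 per sex (half of the n = 82 in 8.1.2): z1 = 0.20/sqrt(0.24 × 2/41) = 1.85.

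| Phase 1 z1 | z2 needed | Chance of a significant female-higher result |
|---|---|---|
| 0.5 | 2.27 | 1.2% |
| 1.0 | 1.77 | 4% |
| 1.28 | 1.49 | 7% |
| 1.85 | 0.92 | 18% |
| Phase 1 not used | 1.96 | 2.5% |

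The chance exceeds 2.5% once z1 is above 2.77 − 1.96 = 0.81. It exceeds 5% once z1 is above 2.77 − 1.645 = about 1.13.

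The Study Summary targets 64 Phase 1 completers. With 64 and 60 subjects and the same 30% versus 50% in Phase 1 (z1 = 1.63), the chance is 13%.

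A simulation with 82 and 78 subjects and a common 40% response rate (400,000 replicates) averages over Phase 1 results:

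- no selection: 2.3%
- Phase 1 leaned female at all: 5.1%
- Phase 1 z above 1: 12.3%
- Phase 2 alone: 2.4% to 2.5% in every case

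**3. What Phase 2 alone can show.** Section 5.3 randomises 90 to placebo and expects about 33% attrition, leaving about 60. With equal sexes and 30% versus 50%:

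- 60 completers (30 per sex): Φ((0.20 − 1.96 × 0.1265)/0.1238) = Φ(−0.387) = 0.35
- all 90 (45 per sex): Φ((0.20 − 1.96 × 0.1033)/0.1011) = Φ(−0.024) = 0.49
- 95% half-width with 30 per sex: 1.96 × sqrt(0.24 × 2/30) = 0.25

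Pooling on target completers does not reach n = 160 either: 64 + 60 = 124, with power 0.63. The 64 is an upper bound, because the share of Phase 1 completers who took placebo is not given.

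**4. Size of the phase confounding.** The shifts below are assumed, with 80 subjects per phase and no true gender effect.

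- Response 40% then 50%, female share 50% then 60%. Females: (40 × 0.40 + 48 × 0.50)/88 = 45.5%. Males: (40 × 0.40 + 32 × 0.50)/72 = 44.4%. Spurious difference: 1.0 point.
- Response 40% then 55%, female share 50% then 65%. Females: (40 × 0.40 + 52 × 0.55)/92 = 48.5%. Males: (40 × 0.40 + 28 × 0.55)/68 = 46.2%. Spurious difference: 2.3 points.

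The planned difference is 20 points.

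**The case against.** The strongest defence has four parts.

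- **Pooling is disclosed and has a reason.** Phase 2 alone has low power, and the plan says that power is why the phases are combined. This stands as a reason to report the pooled estimate. It does not make that estimate a validation, because the pooling was specified after Phase 1 had been analysed by gender.

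- **The source of the hypothesis is not documented.** A reader might infer that Phase 1 prompted the female-higher hypothesis. No sentence says so. Objective 2.1.3 gives no source for the apparent female excess, the Phase 1 findings and conclusions in 1.3 report no gender result, and 8.1.2 introduces the 30% and 50% as an assumption. This objection stands in full. The lack of independence does not rest on that inference, because subjects already analysed by gender re-enter the test either way.

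- **The outcome is largely common to both phases.** A reader might infer that two different outcomes are being mixed. Both phases use app pain ratings, a within-subject permutation rule and the visit 1 to visit 2 baseline, and 8.2 says Phase 2 methods closely follow Phase 1. The documents also expect about 50% responders in each phase. What differs is the length of placebo exposure. The confounding is therefore likely to be minor.

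- **Re-scoring Phase 2 at 2 weeks discards information.** Persistence of the placebo response is a stated aim in 8.2, and the exact Phase 1 window cannot be checked from these documents. This stands, so such scoring belongs in a sensitivity analysis at most.

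It could also be said that the gender question is only exploratory. That does not hold: it is listed with the primary and secondary objectives, has its own endpoint and power calculation, and gates later analyses.

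**Conclusion.** The point holds in a limited form. The pooled gender test re-uses Phase 1 data already examined by gender, so it is not independent confirmation and should not be described as validating the hypothesis.

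The illustrative range is 4% to 18% against a nominal 2.5%. It rests on about 80 subjects per phase, no gender effect in Phase 2, and Phase 1 z values between 1.0 and 1.85, none of which the documents report. A reader might conclude that the false-positive rate is necessarily above 5%, or that it is 18%. Neither is supported. At z1 = 1.0 it is about 4%, at z1 = 0.5 it is below nominal, and the 18% treats a planning assumption as an observed result.

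The missing phase stratum is a minor second issue, worth about 1 to 2 points under the assumed shifts.

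**What to change.** In 2.3.3 and 8.2:

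(a) Report the gender difference in the Phase 2 placebo arm separately, as the only independent evidence. Give its confidence interval (half-width about 25 points) and state its power for 30% versus 50% (about 0.35 with 60 completers, 0.49 with 90).

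(b) Stratify the pooled analysis by phase, for example by Mantel-Haenszel or by logistic regression with a phase term and a phase-by-gender check. Describe the result as supportive, and reword the condition in 8.2 so that a positive pooled result is not called validation.

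(c) Optionally, add a sensitivity analysis that scores Phase 2 response on the first 2 weeks of app ratings, which are already collected.

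The cost is a change of SAP wording and a few extra analyses, with no new patients, visits or measurements. The real price is a more modest gender claim, because the independent test has low power. For 80% power it would need 93 placebo-treated patients per sex, 186 in all, against 90 randomised to placebo.
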